7.6.3 Tools to Assess Exploratory Endpoints

In order to determine which domains of cognition are improved by five consecutive days of tDCS, other objectively assessed cognitive skills will be assessed at the beginning and end of each study wave. Testing will take approximately 40 minutes and will include the following outcomes:

7.6.3.1 Hopkins Verbal Learning Test- Revised (HVLT-R)³. The HVLT-R is designed to evaluate verbal learning and memory. The task takes approximately 8 minutes to complete. Participants attempt to memorize a list of 12 items presented aloud over 3 consecutive learning trials (learning score). After a 20-25 minute delay (during which time other cognitive tests are administered) they are asked to recall as many words as possible (recall score) and to identify word list items from a list of targets and distractors (recognition score). Scores on the learning trial range from 0 – 36, the recall trial from 0 to 12, and the recognition trial from -12 to 12. The HVLT-R has six alternate forms. Scoring and interpretation are simple and outlined in a professional manual. Normative data are available in the form of demographically-adjusted T-scores⁴.

The reliability and validity of the HVLT-R as a measure of new learning and memory has been demonstrated in a variety of patient populations and healthy controls⁶¹. Clinical trials have repeatedly shown it to be sensitive to the impact of cancer and treatment-related neurotoxicities⁶²⁻⁶⁵. It was also recommended for inclusion in a core set of neurocognitive tests by the International Cognition and Cancer Task Force (ICCTF)¹¹. Breast cancer survivors have been shown to produce a mean HVLT-R learning z-score of -0.44 ± 1.23 ⁶³.

7.6.3.2 Brief Visuospatial memory Test (BVMT-R⁴). The BVMT-R serves as the nonverbal analogue to the HVLT-R. Here, participants are presented with six figures on a page for ten seconds. The stimuli are removed and participants are asked to reproduce the figures from memory. As with the HVLT-R, there are three learning trials (learning score). After a 20-25 minute delay (during which time other cognitive tests are completed) they are asked to reproduce the stimuli (recall score) and identify the figures from an array of targets and distractors (recognition score). Scores on the learning trial range from 0 – 36, the recall trial from 0 to 12, and the recognition trial from -6 to 6. The task takes approximately 8 minutes to complete. The BVMT-R has six alternate forms. Scoring and interpretation are simple and outlined in a professional manual. Normative data are available in the form of demographically-adjusted T-scores⁴.

7.6.3.3 Trail Making Test (TMT). The Trail Making Test is composed of two parts (A and B).

Part A is designed to evaluate visual motor scanning and processing speed, while part B is designed to evaluate executive functioning⁶⁶. These tests require patients to connect circles in numerical (part A) or alternating numerical and alphabetical sequence (part B) as quickly as possible. Results are reported as the number of seconds required to complete each part, with higher scores reflecting higher degrees of impairment (range 0 – 300 seconds per trial). Normative data are available in the form of demographically adjusted T-scores^{67,68}. The entire task takes approximately five minutes to complete.

The Trail Making Test²³ is a well-established neuropsychological measure with solid psychometric properties⁶⁹. Clinical trials have repeatedly shown it to be sensitive to the impact of cancer and treatment-related neurotoxicities⁶²⁻⁶⁵. It was also recommended for inclusion in a core set of neurocognitive tests by the ICCTF¹¹. Breast cancer survivors have been shown to produce z-scores of 0.56 ± 1.29 on part A and 0.15 ± 1.22 on part B.⁶³

7.6.3.4 Calibrated Ideational Fluency Assessment (CIFA)⁷. The CIFA verbal fluency trials are designed to evaluate verbal fluency and executive functioning. The task requires patients to name as many words as possible beginning with two different letters (letter fluency) and that belong to two different categories (category fluency) over four separate one-minute trials. The task takes approximately five minutes to complete. Scoring is based on the number of correct words produced over the course of the four trials, with greater values reflecting better performance. Normative data are available in the form of demographically adjusted T-scores⁷.

Tests of verbal fluency are reliable and well-validated tests of cognitive processing^{69,70}. Clinical trials have repeatedly shown verbal fluency performance to be sensitive to the impact of cancer and treatment-related neurotoxicities⁶²⁻⁶⁵. This type of task was also recommended for inclusion in a core set of neurocognitive tests by the ICCTF¹¹.

7.6.3.5 Wechsler Adult Intelligence Scale-Fourth edition (WAIS-IV) Digit Span subtest⁵. The Digit Span subtest assesses simple attention and working memory. Participants are read aloud increasingly lengthy strings of digits and are asked to repeat these strings in forward and backward sequences. The number of digit strings correctly completed forward, backward, and overall serve as outcome measures. The test takes approximately five minutes to complete. Normative data in the form of demographically adjusted scaled scores are available in a professional manual⁷¹.

The Digit Span subtest of the Wechsler scales has excellent psychometric properties and is an extremely well-validated measure of simple attention and working memory⁷¹. It has repeatedly been shown to be sensitive to cancer and treatment-related neurotoxicity⁷²⁻⁷⁴. Normative data are available in the form of demographically adjusted scaled scores. Breast cancer survivors have been shown to produce scaled scores of 10.04 ± 2.67 on the Digit Span test.⁶³

7.6.3.6 Grooved Pegboard Test⁸. The grooved pegboard test is a well-validated test of manual speed and dexterity that has been shown to be sensitive to treatment-related neurotoxicity in breast cancer patients⁷⁵. The test involves placing grooved pegs into

variously oriented holds in a small board as quickly as possible. Participants complete the task with the dominant hand followed by the non-dominant hand. The test takes approximately five minutes to complete. The test is scored according to the number of seconds required to complete the board using each hand (range 0 – 300 seconds per hand). Published normative data are available in the form of demographically-adjusted T-scores.⁶⁸

7.6.4 Patient Reported Outcomes to be assessed at the Beginning and End of each five-day Study Wave
Symptoms of anxiety, depression, sleep quality, and quality of life will be administered prior to and following each five-day study wave (i.e. on four occasions). Testing will take approximately 15 minutes.

7.6.4.1 Hospital Anxiety and Depression Scale (HADS)⁴⁸. Depression and anxiety are common in breast cancer survivors^{49,50} and can negatively affect cognitive functioning including working memory and processing speed⁶⁹ as well as functioning of the DLPFC⁷⁶. In order to determine whether changes in mood or anxiety are contributing to changes in the primary outcome variables, participants will complete the HADS⁴⁸, a brief, well-validated⁷⁷ self-report questionnaire addressing symptoms of anxiety and depression experienced over the previous seven days. In addition to being administered prior to and following each five-day study wave, it will also be administered at both study phone calls (i.e. study days 12 and 47). It takes approximately five minutes to complete.

7.6.4.2 Pittsburgh Sleep Quality Index. In order to control for any differences in sleep quality that may affect fatigue ratings, participants will complete the Pittsburgh Sleep Quality Index prior to and following both five-day active anodal and sham stimulation conditions (i.e. on four occasions)⁷⁸. This questionnaire assesses sleep quality and disturbances over the prior month. It takes approximately 5 minutes to complete.

7.6.4.3 EORTC Quality of Life Questionnaire (QLQ-C30). Quality of life is frequently diminished in breast cancer survivors and is associated with greater rates and severity of fatigue⁷⁹ and depression⁸⁰. In order to control for any differences in quality of life that may affect self-reported fatigue and mood, participants will complete the EORTC Quality of Life Questionnaire (QLQ-C30). This self-report measure assesses health-related quality of life in cancer patients participating in clinical trials. Via five functional scales, three symptom scales, and a global health status measure, the QLQ-C30 addresses physical, role, emotional, cognitive and social functioning as well as symptoms of fatigue, pain, insomnia and others in a 30-item questionnaire. This questionnaire takes approximately 5 minutes to complete.

7.6.5 Additional Assessments
Prior to receiving the first session of active tDCS stimulation or sham stimulation (i.e., at baseline), all participants will spend approximately 30 minutes completing several questionnaires and brief cognitive tests to provide the information necessary to describe our sample characteristics fully and to adjust for participant characteristics in our statistical analyses.

7.6.5.1 History Form. Other characteristics with known associations with performance on tests

of higher-order cognition include illiteracy, English as a second language, educational attainment, occupation, history of learning disabilities, substance abuse and health behaviors that impact cerebral vasculature, other cerebrovascular risk factors, psychiatric and systemic illness and their treatment, traumatic brain injury, family history of several of the above-mentioned variables, and use of disease-modifying drugs and cognitively enhancing drugs such as psychostimulants or caffeine. Conditions associated with fatigue include anemia, thyroid dysfunction and cardiac dysfunction. As such, we will ask participants to complete a history form addressing these issues at the start of their participation. The questionnaire takes approximately five minutes to complete.

- 7.6.5.2 Hopkins Adult Reading Test (HART)⁸¹. Verbal intelligence has been demonstrated to hold moderate correlations with various cognitive abilities. Premorbid IQ is also an important predictor of baseline cognitive dysfunction in cancer patients ⁸². To estimate verbal intelligence, participants will complete the HART at baseline. This test requires participants to read aloud a list of 35 irregularly spelled words. The HART takes approximately 2 minutes to complete. Scoring is based on the number of items correctly pronounced, which is then converted into a standard score based on published normative data⁶⁸.
- 7.6.5.3 Edinburgh Inventory⁸³. A history of left-handedness places one at greater probability of being right hemisphere dominant for language or for being of mixed dominance. Because this investigation seeks to alter some verbally-mediated cognitive abilities, knowledge of one's probability of being left hemisphere dominant for language will be an important consideration. The Edinburgh Inventory specifically assesses handedness and takes approximately 3 minutes to complete.
- 7.6.5.4 UCLA Loneliness Scale⁸⁴. Loneliness is associated with subjective cognitive difficulties in breast cancer survivors⁸⁵. As such, at the beginning of study participation participants will complete the UCLA Loneliness Scale, which addresses one's perceived social isolation and loneliness. This questionnaire takes approximately 5 minutes to complete.
- 7.6.5.5 NEO Five Factor Inventory- 3rd edition (NEO-FFI 3)⁸⁶. Personality characteristics are related to fatigue and other factors in cancer patients, as well as with a tendency to respond to exhibit a placebo effect⁸⁷. At baseline all participants will complete the NEO-FFI 3 in order to assess their standing on the five primary personality factors of openness, neuroticism, extroversion, agreeableness and conscientiousness. This questionnaire takes approximately 10 minutes to complete. Scores for each of the five factors are presented as T-scores.
- 7.6.5.6 TDCS Side Effects. Participants will also complete a brief questionnaire to assess physical sensations and mood experienced prior to and following each stimulation session (i.e. twice during all ten sessions) to document the presence and severity of any tDCS-related side effects. Participants will be asked to rate the severity of these experiences and to report any other sensations they were not asked about directly. At the end of the study each participant will also be asked whether they believed they were receiving active or sham tDCS during each of the two study waves, and they will rate

their degree of confidence with respect to those judgments. This task takes less than five minutes to complete.

NOTE: Please see questionnaires and cognitive tests in Appendices A through U.

7.7 Concomitant and Supportive Therapy

Participation in this study will not disrupt any current care of therapy. The concomitant medications and therapies deemed necessary for the supportive care and safety of the subject are allowed, with the exception of the following:

The use of concurrent medications for fatigue, alertness or sleep will be assessed at the beginning of each study wave and will not be allowed as outlined in the exclusion criteria (above, Section 6.2).

7.8 Discontinuation and Withdrawal of Subjects

All patients who initiate protocol intervention will be included in the overall evaluation of response (intent-to-treat analysis). All reasons for discontinuation of intervention will be documented clearly in the record.

In the event that the intervention is stopped early and unless the subject refuses, follow-up will continue for the planned duration of the study to collect data for the study endpoints.

7.8.1 Discontinuation of Intervention

The reasons for discontinuation of protocol intervention include:

- Unacceptable major toxicity or inability to tolerate the tDCS procedures.
- Intercurrent illness or condition that would, in the judgment of the treating investigator, affect assessment of clinical status to a significant degree or require discontinuation of study intervention.
- Becoming pregnant or starting to nurse.
- Initiating the use of a prohibited medications that may interfere with the efficacy of tDCS.
- At subject's own request. Note: The reason for discontinuation from the study must be documented. The patients will be included in the overall evaluation of response (intent-to-treat analysis) if any protocol intervention was administered prior to withdrawal.
- Study is closed or cancelled for any reason.

7.8.2 Withdrawal from Study

The reasons for withdrawal from the study include:

- Subject withdraws consent for follow-up.
- Subject is lost to follow-up.
- Study is terminated for any reason.

7.9 Additional Information

All participants will be reimbursed for their direct participation, including time spent completing the consent and screening process and time spent completing study interventions, at the rate of \$15.00 per hour or any fraction thereof. In addition, vouchers will be provided for parking in the event the participant is seen at a clinic where she must pay for parking. Reimbursement will be mailed by check at the end of the study (i.e., after both 5 day tDCS/sham sessions; preferred, if acceptable to the subject). If a subject chooses to terminate the testing session early or signs the consent but is ultimately deemed ineligible, she will still be reimbursed for the number of hours she has participated. Reimbursement will not be provided for the time spent during the follow-up telephone calls.

Participants will be involved in a study design that involves several test sessions, across a number of days. To encourage participants to finish the study, there will be an incentive of \$50 at the completion of the final test session (by phone). Of course, as noted before, if a subject should choose not to complete the whole study, she will be paid for the portion(s) completed.

8. STUDY CALENDAR

Procedure	Screening	Intervention							End of Study
		Day(s)							
		1	2-4	5	12 ^b	36	37-39	40	47 ^b
Approximate Duration of Participation (minutes)	12	140	45	115	10	115	45	115	10
Consent, Demographics, Medical and Cancer History	X								
Concomitant Medication and Supplement Use	X					X			
Mini Mental State Exam	X								
CAGE	X								
Quantitative Fatigue Assessment	X								
Transcranial Direct Current Stimulation (active/sham)		X	X	X		X	X	X	
Computerized Working Memory Task ^a		X	X	X		X	X	X	
Paced Auditory Serial Attention Test		X		X		X			X
Functional Assessment of Cancer Therapy Cognitive Scale		X		X	X	X			X
Multi-dimensional Fatigue Symptom Inventory		X		X	X	X			X
Hopkins Verbal Learning Test-Revised		X		X		X			X
Brief Visuospatial Memory Test-Revised		X		X		X			X
Trail Making Test Parts A and B		X		X		X			X
Calibrated Ideational Fluency Assessment		X		X		X			X
WAIS-IV Digit Span Subtest		X		X		X			X
Grooved Pegboard Test		X		X		X			X
Hospital Anxiety and Depression Scale		X		X	X	X			X
Pittsburgh Sleep Quality Index		X		X		X			X
EORTC Quality of Life Questionnaire		X		X		X			X
History Form		X							
Hopkins Adult Reading Test		X							
Edinburgh Inventory		X							
UCLA Loneliness Scale		X							
NEO-Five Factor Inventory - 3		X							
Side Effect Questionnaire ^c		X	X	X		X	X	X	

- a. Computerized working memory task is administered during transcranial direct current stimulation
- b. Day 12 and Day 47 assessments will be performed by phone -1/+3 days of days 12 and 47.
- c. The side effect questionnaire will be completed before and after each transcranial direct current stimulation session (a total of 20 times). On days 5 and 40, participants will be asked if they believed they were receiving active or sham tDCS during the wave they have just completed and to rate their degree of confidence with respect to these judgments.

NOTE: If there is a greater than 21-day period between the screening procedures/determination of eligibility and the initiation of the study intervention, participants will be re-screened during an appointment reminder phone call approximately one week prior to the study intervention. We will permit a between-wave washout period of five rather than four weeks, in which case the second

wave and end of study will be delayed by seven days. The schedule should be followed as closely as is realistically possible; however, the schedule may be modified due to problems such as scheduling delays or conflicts (e.g., clinic closure, poor weather conditions, vacations, etc.) with the guidance of the Principal Investigator/designee, as appropriate, and will not be reportable as a deviation unless the endpoints of the study are affected.

9. ADVERSE EVENTS

In previous studies, a serious adverse event related to tDCS has been defined as that which is caused by tDCS and/or aggravated by tDCS and which results in: irreversible damage to brain tissue, persistent disability or incapacity, unexpected inpatient hospitalization, death or is life-threatening, or medical or surgical intervention to preclude impairment of a bodily function due to tDCS⁴³. Bikson and colleagues recently reviewed the literature on over 33,000 tDCS sessions and 1,000 participants who underwent repeated tDCS sessions⁴³. They found no reports of serious adverse effects or irreversible injury. Similarly, in our experience running over 125 healthy adults and patients through tDCS trials, we have not observed any serious adverse events. There have been a handful of patients who reported mild temporary skin irritation. Adverse events will be assessed through the tDCS Side Effects Questionnaire, which is administered before and after each stimulation session.

It has been demonstrated that tDCS does not: (1) cause heating under the electrodes; (2) result in harmful changes on MRI; or (3) alter levels of serum neuron-specific enolase, a sensitive marker of neuronal damage^{24,88}. Many subjects (up to 71%) perceive a tingling sensation under the electrode during tDCS, although “ramping up” the current can eliminate this perception. Stimulation will be administered via saline-soaked sponge-covered rubber electrodes in order to minimize potentially unpleasant cutaneous sensations during both active and sham stimulation (itching, tingling, etc.). During tDCS, the most common partially adverse effects include mild tingling (71%), moderate fatigue (35%), and light itching under the electrode (30%). Following tDCS, the most common reported adverse effects are headache (12%), nausea (3%), and insomnia (<1%).²⁵ Taken together, all available research suggests that prolonged application should not pose a risk of brain damage when applied according to safety guidelines. There have been rare cases of temporary skin burns related to tDCS; these have all resolved. High electrical impedance at the site of electrode contact could theoretically have been the cause of such burns. The NeuroConn Stimulator Plus monitors electrical impedance and, as a safety precaution, the device terminates current flow if impedance exceeds 55kΩ. The completion of the side effects questionnaire will help determine whether participants experience any negative consequences of the stimulation and will add to the growing literature on tDCS safety and side effects.

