9.1 General

In the case that adverse events related to the study intervention are reported, these will be recorded per the descriptions and grading scales found in the revised National Cancer Institute Common Terminology Criteria for Adverse Events (CTCAE) Version 4.0 for adverse event reporting that can be found at <http://ctep.cancer.gov/reporting/ctc.html>.

Information about all intervention-related adverse events, including those volunteered by the subject verbally or reported by the patient on the tCDS side effect questionnaire, discovered by investigator/study personnel questioning, or detected through other means, will be collected, followed, and reported appropriately.

Only adverse events thought to be related to tDCS will be collected, tracked and reported (as per section 9.2.4 on attribution). The adverse events related to any ongoing treatment for the patients' other medical conditions, including breast cancer, will not be collected.

All adverse events experienced by subjects will be collected from the time of first administration of tDCS (active or sham), throughout the study and until the final study visit. Subjects continuing to experience toxicity believed to be related to tDCS after discontinuation of the study may be contacted for additional assessments until the toxicity has resolved or is deemed irreversible.

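### Side effects are solicited on a schedule only at stimulation sessions, so the last session of each wave and patients who stop early have no timely follow-up form

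*Combined protocol and SAP*

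**What the plan says.** Section 9 (Adverse Events) states: "Adverse events will be assessed through the tDCS Side Effects Questionnaire, which is administered before and after each stimulation session". Note c of the Section 8 calendar fixes the count: "The side effect questionnaire will be completed before and after each transcranial direct current stimulation session (a total of 20 times"). Section 7.6.5.6 agrees, describing sensations and mood "experienced prior to and following each stimulation session (i.e. twice during all ten sessions"). The side effect row of the calendar has no mark at Day 12 or Day 47.

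Those two contacts are telephone calls: "Day 12 and Day 47 assessments will be performed by phone -1/+3 days of days 12 and 47". Section 7.1 describes them as measures of fatigue, mood and cognition. Sections 7.6.2 and 7.6.4.1 name the instruments: FACT-Cog, MFSI-SF and HADS.

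Section 9.1 collects events from the first stimulation "throughout the study and until the final study visit". Its sources are volunteered reports, the questionnaire, questioning by staff, and other means. For toxicity that continues after a patient leaves the study, it says that she "may be contacted for additional assessments until the toxicity has resolved or is deemed irreversible". For patients whose intervention stops early, 7.8 says that "follow-up will continue for the planned duration of the study to collect data for the study endpoints".

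Section 9 also lists effects that appear after stimulation: "Following tDCS, the most common reported adverse effects are headache (12%), nausea (3%), and insomnia (<1"%).

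**The concern.** A form completed straight after a session records what the patient feels at that moment. An effect that begins that evening is recorded on a schedule only if another form follows soon. For the first four sessions of a wave, the next day's pre-session form does this. For the fifth session, which completes the five-day exposure, nothing comparable exists. A patient who stops stimulation has no further sessions and therefore no further forms, even when poor tolerance was the reason.

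Two things are at stake: objective 3.2.2, which is to describe the side effects of tDCS, and routine safety ascertainment. The plan checks whether benefit persists about a week after each wave (objective 3.1.4) but schedules no matching look for harm.

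**Working it through.** **Inputs.** Sessions fall on Days 1–5 and 36–40, and calls on Days 12 and 47 (7.1 and Section 8). There are two forms per session (Section 8, note c). A five-week washout is permitted and delays wave 2 by seven days (Section 8). Enrolment is 50, with 5 expected not to complete (12.2).

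**The plan's own count.** Administrations = sessions × forms per session = 10 × 2 = 20. This matches the stated total and leaves none for the calls. The count gives the same answer as the calendar marks, so the point does not depend on how the table is read.

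**Gap from each session to the next scheduled form.**
- Sessions 1–4 and 6–9 (8 of 10): 1 day.
- Session 5 (Day 5): 36 − 5 = 31 days. With the five-week washout, 43 − 5 = 38 days.
- Session 10 (Day 40): no further form. The end-of-study call comes 47 − 40 = 7 days later, or 6 to 10 days under the calendar window of −1/+3 days.
- Days with no scheduled form: 47 − 10 = 37 of 47 (79%).

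**Patients who stop early: days to Day 47 with no scheduled form.**
- After session 1: 47 − 1 = 46.
- After session 5: 47 − 5 = 42.
- After session 6: 47 − 36 = 11.

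The 5 expected non-completers cover all reasons. The plan does not say how many would stop for toxicity.

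**What other instruments cover.**
- Fatigue and mood: MFSI-SF and HADS at both calls.
- Sleep after wave 1: at the start of wave 2 the Pittsburgh index looks back one month (7.6.4.2), and the QLQ-C30 includes insomnia and pain (7.6.4.3).
- Headache, nausea and skin effects in the week after a wave: no instrument named for the calls is described as covering them.

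**Scale.** The document does not say whether the 12% and 3% are per patient or per session, so both readings are shown as assumptions. In 50 patients, 50 × 0.12 = 6.0 headaches and 50 × 0.03 = 1.5 cases of nausea.
- Per session: up to 6.0 headaches and 1.5 cases of nausea follow the last active session.
- Per patient, spread evenly over five active sessions: 6.0 / 5 = 1.2 and 1.5 / 5 = 0.3.
- For the 25 patients whose last active session is Day 40 (equal allocation assumed), halve these: 3.0 or 0.6 headaches, and 0.75 or 0.15 cases of nausea.

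These are ceilings. Only the share that begins after the post-session form could be missed, and that share is unknown (0 to 100%).

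**The case against.** The strongest reply is that 9.1 promises collection, not a form on every date. It names staff questioning as a route, and staff speak to each patient about a week after each wave. That stands: a reader might infer that nothing outside the form can pick up an event, or that 9.1 is flatly contradicted, and neither follows. What is missing is a set time or script for that questioning, so capture would vary by caller and patient. The final study visit is also undefined. Day 47 is labelled End of Study but is a telephone call. If Day 40 was meant, the conflict for wave 2 narrows, but collection then ends with the last session.

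A reader might also take 7.8 to limit follow-up after early stopping to efficacy data. It does not say so. Section 12.1.3 lists side effects among the exploratory outcomes, so they can count as study endpoints. Reasons for stopping must be documented, and 9.1 requires intervention-related events to be followed. Even so, a form tied to sessions is not scheduled for someone who has no more of them.

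The Day 36 pre-session form does give wave 1 a later look. It comes 31 to 38 days on and is also the baseline for session 6. Its recall period cannot be judged without the content of Appendix U. Attribution in 9.2.4 turns on timing, and only events judged at least possibly related are recorded, so late recall is a weak substitute.

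Two further inferences are tempting. One is that recorded side effects of active tDCS are lowered relative to sham. With balanced sequences, Day 40 is sham as often as active, so the same gap falls on both conditions. The other is that insomnia after Day 5 cannot be detected at all. The Day 36 sleep index covers part of that period.

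**Conclusion.** The scheduling gap is real. Two of ten sessions per patient lack a next-day form: one is followed by a form only after 31 to 38 days, the other by none. Patients who stop early have no scheduled form afterwards. Ascertainment is therefore less complete than the collection window in 9.1 implies, and it differs between waves.

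The consequence is modest. It concerns exploratory objective 3.2.2 and safety reporting; the primary PASAT comparison is untouched. The 6 headaches and 1.5 cases of nausea might be read as events lost, but they are expected totals under an assumed unit, and the number actually missed cannot be derived from the document. No difference in loss between active and sham is shown, given equal allocation to the two sequences, which 7.4 does not state. The change is worth making because it is cheap and uses contacts already planned.

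**What to change.** - **Section 8:** add the side effect questionnaire, or a short version asking about effects since the last stimulation session, to the Day 12 and Day 47 calls. Administrations become 20 + 2 = 22. The first look after wave 1 moves from 31 days to 12 − 5 = 7 days, the longest remaining gap is 36 − 12 = 24 days on the four-week schedule, and the week after Day 40 is covered.
- **Section 7.8:** state that patients who stop stimulation early complete it at their remaining planned contacts, unless they refuse.
- **Section 9.1:** state that collection runs to the Day 47 call (47 + 7 = Day 54 with the five-week washout), in place of the undefined final visit.
- **Call durations:** reconcile and update them. FACT-Cog, MFSI-SF and HADS at about 5 minutes each already total 15 minutes. Section 7.1 gives 15 and the calendar gives 10.

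**Cost.** This is a wording and calendar amendment with no new visit. It adds up to five minutes to each of two calls, which 7.9 does not reimburse, and would record a few more mild events.
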